3 STUDY PROCEDURES

3.1 Patient Selection

The patients in the study must be adults with probable or definite DM or PM according to the Bohan and Peter criteria (Bohan, 1975) and have active disease. Patients will either have low/undetectable or high level of expression of mRNA for type I IFN-inducible genes in whole blood or muscle at the time of screening. High level of expression, defined as a median fold overexpression of the top 25 type I IFN inducible genes of 4-fold or greater, is referred to as gene signature positive, and low/undetectable level of expression is referred to as gene signature negative.

The patient will be counseled by an investigator (physician) or qualified designee who will address the questions and concerns of the patient and secure written informed consent for participation in the study. Written informed consent will be obtained prior to conducting study procedures or administration of study drug.

3.1.1 Inclusion Criteria

Patients must meet *all* of the following criteria:

1. Male or female adults at least 18 years of age at the time of randomization;
2. Written informed consent obtained from the patient or the patient's legal representative prior to receipt of any study medication or beginning study procedures;
3. Probable or definite PM or DM according to the Bohan and Peter criteria (Bohan, 1975);
4. For patients with PM, documentation of a muscle biopsy result that is consistent with the diagnosis of PM;
5. All patients including those with DM must meet at least two of the following criteria:
 - a. Strength in MMT $\geq 80/150$ but $\leq 125/150$ using the MMT-8 muscle group testing (see Appendix A);
 - b. Patient Global Activity Assessment by visual analog scale (VAS) ≥ 2.0 cm on a 10-cm scale, which is included as part of CLINHAQ (see Appendix B);
 - c. Physician Global Activity Assessment by VAS ≥ 2.0 cm on a 10 cm scale, which is included as part of MDAAT (see Appendix C);
 - d. CLINHAQ (see Appendix B) disability index ≥ 0.25 ;
 - e. Global extramuscular activity assessment ≥ 1.0 cm on a 10-cm VAS scale (this measure is the physician's composite evaluation and is based on assessments of activity scores on the constitutional, cutaneous, skeletal, gastrointestinal, pulmonary and cardiovascular scales of the MDAAT [Appendix C]);
6. Subjects with PM must have an elevation of serum CK or aldolase at a minimum level of $1.3 \times$ upper limit of normal (ULN) or serum CK or aldolase at least 2-fold higher than the patient's own lowest value since diagnosis;
7. Subjects with DM must have either an elevated CK or aldolase as above (per inclusion criterion #6) or other laboratory evidence of active myositis. This could include either abnormal signal on skeletal muscle MRI suggestive of inflammation or an electromyogram demonstrated muscle membrane irritability (e.g., fibrillation potentials, positive sharp waves, complex repetitive discharges) and short duration, small amplitude, polyphasic motor unit action potentials.
8. Patients randomized to Dose Cohorts 1, 2, 3A, and 4 must have median fold overexpression of the top 25 type I IFN-inducible genes of 4-fold or greater in whole blood or muscle at the time of screening; patients randomized to Dose Cohort 3B must have low/undetectable expression of type I IFN-inducible genes;
9. Sexually active women, unless surgically sterile (including tubal ligation) or at least 2 years postmenopausal, must use an effective method of avoiding pregnancy (including oral, injectable, transdermal, or implanted contraceptives, intrauterine device, diaphragm with spermicide, cervical cap, abstinence, or sterile sexual partner) in addition to the use of condoms (male or female condoms with spermicide) from screening through end of study. Cessation of birth control after this point should be discussed with a responsible physician. Sexually active males, unless surgically sterile, must likewise practice two effective methods of birth control (condom with spermicide or abstinence) and must use such precautions from Study Day 0 through end of study;
10. Ability to complete the study period, including follow-up period, of up to 350 days; and
11. Willing to forego other forms of experimental treatment during the study.

3.1.2 Exclusion Criteria

Patients must have *none* of the following criteria:

1. Receipt of MEDI-545 in any previous clinical study or prior randomization into the trial;
2. History of allergy or reaction to any component of the study drug formulation;
3. Inclusion body myositis, cancer-associated myositis, myositis associated with another connective tissue disease, environmentally-associated myositis, or drug-related myopathy;
4. A history of or a family history of noninflammatory myopathy, scapular winging, atrophy, or hypertrophy of the calf muscles;
5. Receiving prednisone > 35 mg/day (or an equivalent dose of another corticosteroid) within 14 days before Study Day 0;
6. Receiving the following dosages of medications within 28 days before Study Day 0: hydroxychloroquine > 600 mg/day, mycophenolate mofetil > 3 g/day, methotrexate > 25 mg/week, azathioprine > 3 mg/kg/day, or any dose of cyclophosphamide, cyclosporine, or thalidomide;
7. Have received fluctuating doses of antimalarials, mycophenolate mofetil, methotrexate, leflunomide, or azathioprine within 28 days before Study Day 0 or fluctuating doses of corticosteroids within 14 days before Study Day 0;
8. Have received leflunomide > 20 mg/day in the 6 months prior to Study Day 0.
9. Treatment with any investigational drug therapy within 28 days before Study Day 0 or biologic therapies (eg, rituximab) within 30 days or 5 half-lives of the biologic agent, whichever is longer, before Study Day 0;
10. In the investigator's opinion, evidence of clinically significant active infection, including ongoing, chronic infection, within 28 days before Study Day 0;
11. A history of severe viral infection as judged by the investigators, including severe infections of either CMV or the herpes family such as disseminated herpes, herpes encephalitis, ophthalmic herpes;
12. Herpes zoster \leq 3 months prior to Study Day 0;
13. Evidence of infection with hepatitis B or C virus or HIV-1 or HIV-2, or active infection with hepatitis A, as determined by results of testing at screening;
14. Vaccination with live attenuated viruses within 28 days before Study Day 0;
15. Pregnancy (sexually active women, unless surgically sterile or at least 2 years post-menopausal, must have a negative serum pregnancy test at screening and a negative urine pregnancy test prior to study drug administration on Study Day 0);
16. Breastfeeding or lactating women;
17. History of alcohol or drug abuse < 1 year prior to Study Day 0;
18. History of cancer, except for basal cell carcinoma or carcinoma in situ of the cervix treated with apparent success with curative therapy more than 1 year prior to Study Day 0;
19. History of active TB infection;
20. History of latent TB infection or newly positive TB skin test (reaction defined as \geq 10 mm in diameter if not on systemic immunosuppressive medication or \geq 5 mm if on systemic immunosuppressive medication) without completion of an appropriate course of treatment or ongoing prophylactic therapy;

21. A history of coagulation disorders that in the opinion of the investigator would contraindicate skin or muscle biopsies;
22. Elective surgery planned from the time of screening through Study Day 196;
23. At screening blood tests (must be within 28 days before Study Day 0) any of the following:
 - Serum creatinine > 4.0 mg/dL,
 - Neutrophils < 1,500/mm³,
 - Platelet count < 50,000/mm³;
24. History of any disease, evidence of any current disease (other than DM or PM), any finding upon physical examination, or any laboratory abnormality, that, in the opinion of the investigator or medical monitor, may compromise the safety of the patient in the study or confound the analysis of the study; or
25. Any employee of the research site who is involved with the conduct of the study.

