3.4.5 Concomitant Medications

All concomitant medications, including herbal products, used by the patient from screening through Study Day 350 will be recorded on the case report form. The concomitant administration of IVIG is allowed.

Patients may not receive the following from screening through Study Day 350:

1. Investigational agents (eg, rituximab for myositis);
2. Any live attenuated virus vaccine;
3. Hydroxychloroquine > 600 mg/day, mycophenolate mofetil > 3 g/day, methotrexate > 25 mg/week, leflunomide > 20 mg/day, azathioprine > 3 mg/kg/day; or
4. Any dose of cyclophosphamide, cyclosporine, or thalidomide.

Corticosteroid doses may not exceed 35 mg/day of prednisone or an equivalent dose of another corticosteroid. Corticosteroid doses must remain constant from 14 days before Study Day 0 through Study Day 196. Thereafter, corticosteroid doses may be increased, tapered, and discontinued as considered appropriate by the investigator.

Patients may receive medications to treat adverse events as deemed necessary by the investigator or the patient's physician.

See Section 3.4.2 for guidance in handling clinical deteriorations.

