Extramuscular Activity Assessment (MDAAT)		X	X ^c	X		X				X		X		X		
Pulmonary Function Tests ⁿ		X								X ^o						
Physician Global Activity Assessment ^p		X	X ^c	X		X				X		X		X		
CLINHAQ ^q		X	X ^c	X		X				X		X		X		
Patient Global Activity Assessment ^q		X	X ^c	X		X				X		X		X		
Myositis Damage Index			X ^c							X						
SF-36v2			X ^c							X						
WPAI:SHP Questionnaire			X ^c							X						
Pruritus VAS ^r			X ^c	X		X				X		X		X		
CDASI ^r			X ^c	X		X				X		X		X		
DLQI ^r			X ^c							X						
Skin Photographs ^{r,s,t}			X ^c	X		X				X		X		X		

Table 4 Schedule of Patient Evaluations (Screening and Treatment Period)

Study Day	Visit	Screen ^b	Treatment Period													
			0	14	28	42	56	70	84	98 ^a	112	126	140	154	168	182
			1	2	3	4	5	6	7	8	9	10	11	12	13	14
CORRELATIVE STUDIES																
Serum for Exploratory Research and Storage ^{j, s}			X ^b		X		X			X		X		X		
Serum for autoantibodies ^j			X ^b							X						
Whole Blood for IFN Gene Expression Analyses		X	X ^b		X		X			X		X		X		
Peripheral Blood for Flow Cytometry ^{j, u}			X ^b							X						
Muscle Biopsy ^w			X ^b							X						
Punch Skin Biopsy ^{r, s}			X ^b							X						
Whole Blood for DNA Sample ^s				X												
PK/IM																
MEDI-545 Serum Level ^j			X ^v	X	X	X	X	X	X	X ^v	X	X	X	X	X	X ^v
Anti-MEDI-545 Antibodies ^j			X		X		X			X		X		X		

Table 4 Footnotes:

- a. If a patient discontinues his or her participation in the study prior to Study Day 98, the assessments designated for Study Day 98 will be performed at the discontinuation visit. If a particular assessment has been performed within 2 weeks before the discontinuation visit, it need not be repeated, except if follow-up muscle and skin biopsies have been done at any time, they need not be repeated. (If a patient discontinues after Day 98, see Table 5 footnotes a and b.)
- b. Obtain within 28 days prior to Study Day 0.
- c. Assessments may be performed up to 72 hours prior to dosing on Study Day 0, except muscle and skin biopsies and skin photographs, which may be performed up to 28 days prior to Study Day 0. The open muscle biopsy may be done as part of screening to meet inclusion criteria as long as the dose(s) of immunosuppressive medications have been stable for one month and will remain the same as that in Day 0.
- d. Medical history includes history of viral reactivation events.
- e. Chest x-ray taken within 6 months of screening is considered suitable for screening and need not be repeated.

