 - CLINHAQ (includes Patient global activity assessment)

Study Day 0: First Dose

Visit 1

1. Verify eligibility criteria
2. Update screening history and physical examination (any new findings since screening)
3. Body weight
4. Randomization and assignment of PID
5. Record concomitant medications
6. Urinalysis, includes collection of urine for β HCG (for women who are sexually active and are not surgically sterile or at least 2 years postmenopausal; this test must be negative for study participation)
7. Baseline blood collection
 - Chemistry panel

- CBC with differential and platelet count
 - Serum for safety biomarkers
 - Serum levels of muscle enzymes
 - Serum for exploratory research (including IFN- α assay and proteomics) and storage
 - Serum for autoantibodies (including ANA, anti-SSA, anti-RNP, anti-Jo-1, anti-SRP, anti-Mi-2 antibodies)
 - Whole blood for IFN gene expression analysis
 - Peripheral blood for flow cytometry
 - MEDI-545 serum level
 - Anti-MEDI-545 antibodies
8. Viral surveillance testing (including EBV, CMV, HSV, and HPV)
 9. Disease activity assessments:
 - MMT
 - Extramuscular activity assessment
 - Physician global activity assessment (included as part of MDAAT)
 - CLINHAQ (includes Patient global activity assessment)
 - Myositis Damage Index
 - SF-36v2
 - WPAI: SHP questionnaire
 - Pruritus VAS (DM patients only)
 - CDASI (DM patients only)
 - DLQI (DM patients only)
 10. Skin photographs (optional, DM patients only, preferably prior to the punch skin biopsy and within 28 days before the visit)
 11. Muscle biopsy (within 28 days before the visit). The open muscle biopsy may be done during screening to address inclusion criteria as long as the dose(s) of immunosuppressive medications have been stable for one month and will remain the same as that in Day 0. Muscle for IFN gene expression analysis
 12. Punch skin biopsy (optional punch biopsy, DM patients only, within 28 days before the visit). Skin for IFN gene expression analysis
 13. Vital signs up to 30 minutes before administration of study drug
 14. Administration of study drug
 15. Monitor vital signs approximately every 15 minutes during administration of the drug, immediately after the infusion (within 10 minutes after the infusion has stopped), and approximately every 30 minutes after the completion of the infusion until stable. Measure blood pressure and heart rate prior to discharge from the site.

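### Corticosteroid dose is fixed only from Day -14, but the skin biopsy, a baseline-only muscle biopsy and the cohort-setting blood signature may be taken from Day -28

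*Protocol*

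**What the plan says.** **Steroid rules.** Exclusion 7 in Section 3.1.2 rules out patients with "fluctuating doses of corticosteroids within 14 days before Study Day 0". Section 3.4.5 sets the same start: "Corticosteroid doses must remain constant from 14 days before Study Day 0 through Study Day 196". Exclusion 5, on the size of the dose, looks back over the same period: "Receiving prednisone > 35 mg/day (or an equivalent dose of another corticosteroid) within 14 days before Study Day 0". For antimalarials, mycophenolate, methotrexate and the rest, exclusion 7 asks for twice as long: "leflunomide, or azathioprine within 28 days before Study Day 0".

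**Sampling windows.** Table 4 footnote c exempts muscle and skin biopsies from the 72-hour baseline window; they are procedures "which may be performed up to 28 days prior to Study Day 0". The Day 0 visit list and Section 3.6.7.3 repeat the 28 days. Screening blood, including the sample for interferon gene expression, also has a 28-day window (Table 4 footnote b and the Screening list in Section 3.5).

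**The one dose condition attached to a sample.** Footnote c and Day 0 item 11 allow the open muscle biopsy to serve the inclusion criteria during screening, "as long as the dose(s) of immunosuppressive medications have been stable for one month and will remain the same as that in Day 0".

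**Use of the samples.** Signature status in whole blood or muscle decides between Cohort 3B and the signature-positive cohorts (inclusion criterion 8; Section 3.2). Muscle and skin are biopsied once at baseline and once at Day 98.

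**The concern.** Footnote c shows that the authors saw the difficulty: a biopsy read at one level of immunosuppression is a poor baseline for treatment given at another. The condition is nevertheless attached to one use of one sample. The skin biopsy, a muscle biopsy taken only as the baseline, and the signature blood sample share the 28-day window without it.

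Section 1.1 calls corticosteroids the mainstay of treatment and says that immunosuppressives reduce tissue inflammation. A steroid change between the biopsy and Day 0 could therefore move histology and infiltrate staining by itself. The change from baseline to Day 98 would then mix study drug with that earlier change. With 6 active and 2 placebo patients planned per cohort, randomization cannot be relied on to balance it.

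**Working it through.** No sample size or power figure is involved. The check compares day windows.

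**Length of the gap**
- Corticosteroids: 28-day sampling window minus 14-day stability window = 14 days (Day -28 to Day -15).
- Other immunosuppressives named in exclusion 7: 28 - 28 = 0 days.

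The gap concerns corticosteroids only.

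**Which samples fall in it**

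| Sample | Earliest day | Dose condition on the sample | Measured again on Day 0? | Left open |
|---|---|---|---|---|
| Open muscle biopsy used for inclusion | -28 | Footnote c | No | Nothing, if immunosuppressive medications include corticosteroids |
| Muscle biopsy solely as baseline | -28 | None clearly stated | No | Baseline may be at another steroid dose |
| Skin biopsy (optional, DM only) | -28 | None | No | Same |
| Screening blood signature | -28 | None | Yes, but the result has already gone to the IVRS | Cohort assignment only |

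**A path through the rules.** Take a DM patient who never exceeds 35 mg/day. The skin biopsy and signature blood are taken on Day -28, the steroid dose is changed on Day -20, and it is constant from then on. Exclusions 5 and 7 and Section 3.4.5 are all met. The Day 98 skin biopsy is taken at the Day 0 dose and the baseline biopsy was not. No later baseline tissue is scheduled to replace it.

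**Mismatch of periods.** If corticosteroids count as immunosuppressive medication, as Section 1.1 suggests, footnote c asks for one month of stability where exclusion 7 and Section 3.4.5 ask for 14 days. The documents do not say which governs a biopsy that serves both as inclusion evidence and as baseline.

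**Weight of one patient.** In a cohort of planned size, one mismatched pair is 1/6 = 17% of the active pairs or 1/2 = 50% of the placebo pairs. One patient assigned on a changed signature would be 1/8 = 12.5% of Cohort 3B. These are weights per patient, not estimates of how many are affected.

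**The case against.** The strongest reply is Section 3.4.2, which says patients should stay on the doses they were taking at consent. Consent precedes every study procedure, so a dose changed after sampling departs from that instruction. This stands in part. However, the instruction is worded as *should* and speaks of the treatment period, while the mandatory rule in Section 3.4.5 begins at Day -14. It softens the gap and does not close it.

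Several stronger readings might be inferred, and the documents do not support them:

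- *All baseline biopsies are uncontrolled.* No. A muscle biopsy used for inclusion is covered. Muscle signature is itself part of criterion 8, so a cohort assigned on muscle is covered too.
- *The blood pharmacodynamic baseline and the disease activity scores are affected.* No. Both are measured again within 72 hours of the first dose, and Section 5.1 takes the last valid pre-dose value as baseline.
- *Doses well above 35 mg/day are allowed at sampling because exclusion 5 looks back only 14 days.* Doubtful. The cap in Section 3.4.5 carries no Day -14 limit and follows restrictions that run from screening.
- *A steroid change would move patients across the 4-fold cut.* Nothing in the protocol shows this. Misassignment is a possibility to check.

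It is also fair that 14 days for steroids and 28 for other agents looks deliberate, that the skin biopsy is optional, and that concomitant medication is recorded from screening, so dose at sampling can be recovered. The last point makes the remedy cheap; it does not remove the inconsistency. A listing and a sensitivity table could sit in an SAP, and their absence from the protocol is not the complaint.

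**Conclusion.** The concern holds in a limited form. For 14 days of the sampling window, no mandatory rule ties the steroid dose at a skin biopsy, a baseline-only muscle biopsy or the screening signature sample to the dose on Day 0. For tissue, this can put a pre-treatment steroid change inside the baseline-to-Day 98 comparison. For blood, it bears only on which cohort the patient enters.

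The affected results are exploratory and descriptive. The primary safety assessment is not touched, and the number of patients affected cannot be derived from the protocol. The conclusion assumes that immunosuppressive medications in footnote c include corticosteroids, and that footnote c means what it says in tying its condition to inclusion use. It is worth correcting, and is not a critical defect.

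**What to change.** 1. Reconcile Table 4 footnote c, Section 3.4.2, exclusion 7 and Section 3.4.5, so that one statement says when the dose must be stable and for which samples. Which period is right is a clinical decision for the sponsor.
2. Apply footnote c's same-dose-as-Day-0 condition to every baseline muscle and skin biopsy and to the screening signature sample. Meet it by scheduling the sample within the stable period. Do not repeat a biopsy for this purpose.
3. For patients already enrolled (51 had been dosed by the cut-off in Section 1.5), list corticosteroid dose at each baseline sample against dose on Day 0, and repeat the tissue summaries without mismatched pairs.
4. Report how often the Day 0 blood signature disagrees with the screening status that set the cohort. Both blood samples are already scheduled.

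The cost is a sentence in footnote c and in the Day 0 visit list, one listing, one sensitivity table and one count. Scheduling becomes slightly tighter: a later signature sample leaves less time to report the result to the IVRS before Day 0. Patients whose dose is already stable can still be sampled from Day -28.

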3.2 Patient Randomization Procedures and Treatment Allocation

Patients will be screened by investigators or qualified designees to assess eligibility for randomization into the study. Screening of patients will be managed so that about 40% to 60% of randomized patients will have DM and the remainder PM. A master log will be maintained of all consented patients and will document all screening failures, including the reason for screening failure.

Treatment assignments will be determined using a central randomization procedure through an interactive voice response system (IVRS). Patients with a median fold overexpression of the top 25 type I IFN inducible genes of 4-fold or greater in whole blood or muscle will be randomized to Dose Cohorts 1, 2, 3A, or 4, and patients with low/undetectable expression of type I IFN-inducible genes will be randomized to Dose Cohort 3B. Central randomization will be applied without regard to site.

The randomization procedure is as follows:

- Investigator or qualified designee confirms the patient meets all eligibility criteria and has signed an informed consent;
- MedImmune calls the IVRS before Study Day 0 to provide the results of type I IFN gene signature in the patient;
- The IVRS notifies the investigator or qualified designee that the patient may be randomized into the study;
- Investigator or qualified designee calls the IVRS on Study Day 0 and provides at a minimum the initials, date of birth, body weight of the patient, and the clinical diagnosis;
- The IVRS randomly assigns a treatment (MEDI-545 or placebo) to the patient along with a PID and blinded study drug kit number to be used for that patient; and
- A confirmatory fax or e-mail with this information is sent to the investigator or qualified designee.

When a patient is assigned a PID by the IVRS the patient is considered randomized into the study.

Patients will be dosed with either MEDI-545 or placebo on Study Day 0. In each of the 5 dose cohorts, if one of the first 8 patients is randomized but not treated, or not evaluable, the treatment assignment for this replaced patient will be used for the 9th patient enrolled in this cohort. If there are additional patients who are replaced, the replaced patient's treatment assignments will be used in order of enrollment. A dose cohort may be expanded by up to 4 additional patients (for a maximum of 20 additional new patients in total) if eligible patients are in screening at the time 8 patients have been randomized into the dose cohort.

Decisions relating to dose escalation will be made by the sponsor based on review of blinded cumulative safety data by the Medical Monitor (see Section 4.9). The safety data will also be reviewed on a regular basis by the Safety Monitoring Committee (SMC), which can stop study entry and dosing. The SMC includes physicians who are independent from MedImmune. The sponsor will notify the sites when randomization in each dose group is completed and when randomization into the next dose group is permitted.

